**Time Period for Vital Status**

The period for capturing vital status begins at the date of randomization. The end of this time period is defined as follows:

- For all subjects known to have died, use the date of death
- For all subjects who complete the study, use the study completion date (see Section 14.6.1)
- For all subjects who withdraw from the study, but vital status has been ascertained, *and are known to have not died* – use the latest date last known to be alive. If vital status has not been ascertained following study withdrawal, use the study withdrawal date

Any endpoints that occurred before the start of this time period are considered to be prior to the time period for vital status, and any endpoints that occurred after the end of this time period are considered to be post the time period for vital status.

**Time Period for On-treatment Cardiovascular Endpoints**

The period for capturing on-treatment CV safety endpoint events begins at the treatment start date. The end of this time period is defined as follows:

- For subjects whose last non-zero dose date is missing and who took study treatment, use date of study withdrawal/completion
- For subjects continuing on study past the last non-zero dose date +28 days, use (last non-zero dose date + 28)
- For subjects whose study withdrawal/completion date is on or before (last non-zero dose date +28), use date of study withdrawal/completion

If the censoring date as defined above for on-treatment CV safety endpoints is after the censoring date as defined for the analysis during the time period for follow-up of CV safety endpoints, then use the censoring date for the analysis during the time period for follow-up of cardiovascular endpoints.

CONFIDENTIAL

204837

**Evaluation Time Periods for CV Endpoints**

Any endpoints that occurred before the start of this time period are considered to be prior to the time period for on-treatment cardiovascular safety endpoints, and any endpoints that occurred after the end of this time period are considered to be post the time period for on-treatment cardiovascular safety endpoints.

**14.6.4.2. Blood Pressure Endpoints****Blood Pressure Endpoints****Pre- and Post- Dialysis BP**

- Unless otherwise specified, for summaries and analyses of BP values, the post-dialysis BP values will be used.

**End of Treatment BP Value**

- See Section [14.6.1](#)

**Mean Arterial Pressure (MAP)**

- $MAP = [(2*DBP)+SBP]/3$

**Blood Pressure Exacerbations**

- BP exacerbations will be defined as (SBP  $\geq$  25 mmHg increase from baseline or SBP  $\geq$  180 mmHg or DBP  $\geq$  15 mmHg increase from baseline or DBP  $\geq$  110 mmHg) and grouped by type as follows:
  - BP exacerbations
    - SBP exacerbations
      - SBP  $\geq$  25 mmHg increase from baseline or
      - SBP  $\geq$  180 mmHg
        - SBP  $\geq$  180 mmHg and baseline SBP < 180 mmHg (including subjects with a missing baseline SBP)
        - SBP  $\geq$  180 mmHg and baseline SBP  $\geq$  180 mmHg
    - DBP exacerbations
      - DBP  $\geq$  15 mmHg increase from baseline or
      - DBP  $\geq$  110 mmHg
        - DBP  $\geq$  110 mmHg and baseline DBP < 110 mmHg (including subjects with a missing baseline DBP)
        - DBP  $\geq$  110 mmHg and baseline DBP  $\geq$  110 mmHg

**Notes:**

- BP values used to assess BP exacerbations must be on-treatment (see Section [14.4.1](#)), unless otherwise specified.
- BP values used to assess BP exacerbations can be scheduled or unscheduled.
- For visits where BP is measured in triplicate, the average of the 3 BP values will be used to assess BP exacerbations.
- BP exacerbations identified using post-dialysis BP values will be used in summaries and analyses of BP exacerbations, unless otherwise specified.
- Subjects with multiple exacerbation events on the same calendar date for each type defined above are considered to have one exacerbation event for event counts by type. For example, a subject with a SBP and a DBP exacerbation on the same date would count in each of the SBP and DBP types, but would only count as one BP exacerbation event in the total BP exacerbation type.

CONFIDENTIAL

204837

Blood Pressure Endpoints
Blood Pressure Exacerbation Event Date

 
Date of BP exacerbation
 

On-Treatment BP Medication

 
See Section 14.4.1 for treatment states for concomitant medications.
 

General

 
Censored time (days) = last non-zero dose date– treatment start date + 1
 
BP exacerbation person years = (cumulative total of censoring time for all subjects) / 365.25
 
BP exacerbation event incidence rate (per 100 person years) = (100 * number of BP exacerbations) / BP exacerbation person years
 

Changes in Blood Pressure Medications

 
No change: no new anti-hypertensive records since baseline (day before study treatment start date) and no change to anti-hypertensive records from baseline until date of visit while on study treatment.
 
Increase: addition of new anti-hypertensive records for any reason or a change with a primary reason for changing dose/frequency or stopping of ‘increased to...’ since baseline until date of visit while on study treatment
 
Decrease: discontinuation of an anti-hypertensive record with primary reason for change starting with “discontinued” or a change with a reason of ‘Decreased due to...’ since baseline until date of visit while on study treatment
 
Switch = change with a reason of ‘switched to another agent.’ since baseline until date of visit while on study treatment
 

Cumulative Changes in Blood Pressure Medications

 
For the summary of cumulative changes excluding “Once only” and “PRN” records, cumulative change will be counted from the date of first study treatment to the Week 52 visit date while on study treatment. If a new anti-hypertensive medication is added during this time, it will be counted as one change. If the medication also stops during this period, then it will count as two changes (one change due to starting, and one change due to stopping). The cumulative number of changes will be calculated by adding up the changes for all records during this time period. The same steps will be repeated for the period starting from the date of first study treatment to End of Treatment
 
For the summary of cumulative changes for “Once only” records only, cumulative change will be counted from the date of first study treatment to the Week 52 visit date while on study treatment. Since “Once only” doses will have same start and stop dates, a new anti-hypertensive medication record during this period will be counted as one change. As “once only” doses are likely administered to control BP during dialysis, so they are considered part of a single titration regimen, hence multiple “once only” records on the same date will be counted as one change. The same steps will be repeated for the period starting from the date of first study treatment to End of Treatment
 

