
 • To compare the effect of daprodustat administered three-times weekly to epoetin alfa on BP and BP medication changes 	
 • Observed and change from baseline in SBP, DBP and MAP by visit • Number of BP medications per participant by visit • Change from baseline in the number or dose of BP medications per participant by visit • N (%) of participants who had no change in the number or dose of BP medications from baseline by visit • N (%) of participants who had an increase in the number or dose of BP medications from baseline by visit • N (%) of participants who had a decrease in the number or dose of BP medications from baseline by visit

 • To further compare the effect of daprodustat administered three-times weekly to epoetin alfa on Hgb variability 	
 • Hgb observed and change from baseline across all visits • % of time Hgb is above, within and below the analysis range of 10 to 11.5 g/dL during the EP • Number (%) of participants with mean Hgb

Objectives	Endpoints
	
above, within and below the Hgb analysis range during the EP
 
 • Number (%) of participants with a Hgb <7.5 g/dL during the EP • Number of times Hgb <7.5 g/dL during the EP • Number (%) of participants with a >1 g/dL increase in Hgb within any 2-week period (assessed at Week 2 through Week 8), or with a >2 g/dL increase in Hgb within any 4-week period up to Week 52 • Number (%) of participants with a >1 g/dL decrease in Hgb within any 2-week period (assessed at Week 2 through Week 8), or with a >2 g/dL decrease in Hgb within any 4-week period up to Week 52 • N (%) of participants with a Hgb value \geq12 g/dL during the EP • Number of times Hgb \geq12 g/dL during the EP • % of time Hgb \geq12 g/dL during the EP

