### Planned Exploratory Displays

- Observed and change from baseline in SBP, DBP, and MAP by visit are included in the summary of secondary safety analyses described in Section 8.1.
- The last on-treatment BP parameter change from baseline value (SBP, DBP, and MAP) recorded prior to the first change in BP medications will be summarized using mean, standard deviation, minimum, P25, median, P75, and maximum by treatment group. The first change in blood pressure medication occurs at the earliest time a new anti-hypertensive medication is administered or if the dose or frequency of an existing blood pressure medication is changed for any reason (increased, decreased, discontinued, or switched to another agent) in any anti-hypertensive medication, except medication records with frequencies of “Once only” and “PRN.”
- Number of BP medications per subject while the subject was on treatment will be summarized using mean, standard deviation, minimum, P25, median, P75, and maximum for each scheduled visit by treatment group. Number of BP medications for each subject at baseline is defined as the number of medications taken on the day before study treatment start date. For end of treatment, it is defined as the number of medications taken on last non-zero dose date + 1 day. The number of BP medications at all other nominal visits is defined as the number of medications taken on the day of the visit. Medication records with frequencies of “Once only” and “PRN” will be excluded from this summary.
- Change from baseline in the number of BP medications per subject while the subject was on treatment will be summarized using mean, standard deviation, minimum, P25, median, P75, and maximum for each scheduled visit by treatment group. The number of BP medications at baseline, end of treatment and all other nominal visits will be defined as described in the previous paragraph. Medication records with frequencies of “Once only” and “PRN” will be excluded from this summary.
- Additionally, the number and percentage of subjects who had no change, at least one change, an increase, a decrease, or a switch in the dosage or number of BP medications from baseline while the subject was on treatment will be summarized for each scheduled post-baseline visit by treatment group (see Section 14.6.4 for details of classifying BP medication changes). Medication records with frequencies of “Once only” and “PRN” will be excluded from this summary.

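### The SAP rule for an increase in BP medication also counts the replacement drug in a one-for-one switch, which inflates the Increase row of Table 3.047

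*SAP*

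**What the plan says.** Protocol Section 4 lists the exploratory endpoint as "N (%) of participants who had an increase in the number or dose of BP medications from baseline by visit", with parallel endpoints for no change and for a decrease.

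SAP Section 8.2 (Blood Pressure and Blood Pressure Medication Change) plans a by-visit summary, Table 3.047. Besides rows for participants whose medication stayed the same or changed in any way, it has rows for those with "an increase, a decrease, or a switch in the dosage or number of BP medications from baseline while the subject was on treatment". It refers to Section 14.6.4 for the classification.

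Section 14.6.4.2 then gives four rules, each running from baseline to the visit date while on study treatment:

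- **No change:** "no new anti-hypertensive records since baseline (day before study treatment start date) and no change to anti-hypertensive records".
- **Increase:** "Increase: addition of new anti-hypertensive records for any reason". A second criterion covers an altered or stopped record whose stated reason denotes an increase.
- **Decrease:** "discontinuation of an anti-hypertensive record with primary reason for change starting with" a discontinuation term, or a change whose reason is a reduction.
- **Switch:** "Switch = change with a reason of" a move to a different agent.

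The only records left out of the by-visit summary are one-off and as-needed entries. Nothing ranks the categories, makes them exclusive, or pairs a stopped record with its replacement.

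**The concern.** The Increase row should show how many participants had their BP treatment stepped up. Decrease and Switch depend on the recorded reason, but the first criterion for Increase expressly ignores it. A participant moved from one drug to another, with nothing added, therefore appears as stepped up.

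The row bears on a question the programme cares about. Protocol Section 3.3.2 names treatment of anemia without rhEPO-related hypertension as a potential benefit, and the SAP added worsening of hypertension to the adverse events of special interest. Blood pressure results are easier to read when one knows whether antihypertensive treatment was intensified. A row that mixes intensification with substitution answers that less well.

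**Working it through.** The plan states no figure for this row, so there is nothing to reproduce. The check applies the four rules to simple record patterns and compares the result with the protocol endpoint. It assumes that a different drug is entered as its own record.

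| Pattern | Drugs before → after | SAP categories met | Protocol increase in number or dose? |
|---|---|---|---|
| A stopped for a switch, B started | 1 → 1 | Switch **and** Increase | Number unchanged; no increase recorded |
| B added, A kept | 1 → 2 | Increase | Yes |
| A's dose raised within its record | 1 → 1 | Increase | Yes |
| A's dose lowered within its record | 1 → 1 | Decrease | No |
| A discontinued, nothing started | 1 → 0 | Decrease | No |

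Only the first line goes wrong.

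1. **No offset.** A was stopped with a switch reason, which meets neither part of the Decrease rule. B's start counts as an Increase, while A's stop counts only as a Switch. The Increase row can therefore only be inflated by switches.
2. **Carry-forward.** Each category looks back from the visit to baseline, so one early switch marks the participant as an Increase at that visit and at every later on-treatment visit.
3. **Unaffected rows.** A switch is a real change. The participant rightly leaves the no-change row and enters the any-change row, whatever happens to Increase.
4. **Unaffected tables.** Tables 3.045 and 3.046 count the drugs taken on the visit day, so a completed one-for-one switch nets to zero.

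**Size.** Let i be the share with a true increase and s the share with a switch but no true increase. The reported Increase is i + s. The documents give neither, so these are assumed values:

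- i = 20%, s = 5%: 20 + 5 = 25% reported.
- i = 20%, s = 15%: 20 + 15 = 35% reported.

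For two arms with true increases of 20% and 30% and s = 15% in each, the reported values are 35% and 45%. The difference stays at 10 points (30 − 20 = 10; 45 − 35 = 10). The ratio moves from 20/30 = 0.67 to 35/45 = 0.78. If s differs between arms, the reported difference moves by the difference in s; the documents give no basis for guessing that.

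**The case against.** The strongest reply is that little depends on this. The endpoint is exploratory with no testing planned, and the secondary BP analyses (change in SBP, DBP and MAP, and BP exacerbations) do not use the definition. The Switch row stands beside the Increase row, so affected participants are double-counted and not hidden. Tables 3.045 and 3.046 show the number of drugs correctly. With equal switching the absolute difference is preserved, and the SAP plans no ratio for this table. All of this stands, and it limits the consequence. It does not make the Increase row correct: the medication-count tables carry no dose information, and they do not give the number of participants with an increase, which is what the protocol names.

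A reader might also infer that dose reductions are reported as increases, so that the comparison between arms could change sign. That requires a lower dose to be entered as a new record, which the documents do not show. The text points the other way: the no-change rule separates new records from changes to records, dose changes have their own criteria, and Section 8.2 distinguishes a new medication from a changed dose of an existing one. The sign-reversal reading is not supported.

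Nor do the documents support saying that the direction of BP treatment is lost altogether, given the medication-count tables and the separate Switch and Decrease rows.

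The cumulative summary, Table 3.048, shows increase, decrease and switch as reasons, but the cumulative rule in Section 14.6.4.2 counts starts and stops and does not invoke the by-visit Increase definition. Carry-over to that table is plausible but not stated.

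**Conclusion.** The point holds for switches. As written, the rule counts every one-for-one switch to a newly recorded drug as an increase, contrary to the protocol endpoint, in one direction only, and at every later on-treatment visit in Table 3.047. The excess equals the share of participants who switched without a true increase, which the documents do not give.

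The consequence is modest. It concerns one row of an exploratory, untested descriptive table. The primary and principal secondary analyses, the secondary BP analyses, the no-change and any-change rows, and Tables 3.045 and 3.046 are untouched. The conclusion rests on reading the rule literally and on a new drug having its own record. It is still worth correcting, because a stated rule miscounts a protocol-named endpoint and the correction is cheap.

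**What to change.** In SAP Section 14.6.4.2:

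- Exclude from Increase a new antihypertensive record that replaces one stopped or changed because of a switch to a different agent. Count it under Switch only, unless an increase is separately recorded.
- Identify replacements from the recorded reasons for change and for addition, which Protocol Section 7.7 says are collected for antihypertensives, with start and stop dates as support. A fixed date window alone would miss overlapping or delayed switches.
- State whether the categories are mutually exclusive.
- Apply the same rule to the increase, decrease and switch rows of Table 3.048 if they use this classification.
- Check the eCRF. If a dose reduction is entered as a new record of the same drug, exclude that record from Increase too.

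The cost is a short change of wording and one step in programming, with no new data. The small downside is that a step-up made through a switch, with no recorded increase, would appear only as a Switch.

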#### 14.6.4.3. Adverse Events

Adverse Events
AEs of Special Interest
Adverse events of special interest are classified as follows:

**Adverse Events**

- Death, myocardial infarction (MI), stroke, heart failure, thromboembolic events, thrombosis of vascular access
- Thrombosis and/or tissue ischemia secondary to excessive erythropoiesis
- Cardiomyopathy
- Pulmonary artery hypertension
- Cancer-related mortality and tumor progression and recurrence
- Esophageal and gastric erosions
- Proliferative retinopathy, macular edema, choroidal neovascularization
- Exacerbation of rheumatoid arthritis
- Worsening of hypertension

Potential AESIs will be identified through a pre-defined terms of interest process in which pre-defined lists of AE preferred terms corresponding with each AESI will be used to identify events considered to be potential AESIs. Sites will be prompted via query to complete any necessary additional information for these AESIs in the eCRF.

For the category of thrombosis and/or tissue ischemia secondary to excessive erythropoiesis, after the terms of interest list has been applied, the additional Hgb criteria described below will be applied to identify only those events that are considered to be secondary to excessive erythropoiesis as meeting the AESI definition for thrombosis and/or tissue ischemia secondary to excessive erythropoiesis.

Thrombosis and tissue ischemia events will be considered to be secondary to excessive erythropoiesis if during the window of [AE start date – 30 days, AE start date +15 days] any one of the following 3 events occurs:

- Any Hgb value  $\geq$  13 g/dL (measured pre-dialysis)
- Hgb increase  $>$  2 g/dL over 2 weeks (+1 week)
  - Note: for programming purposes, a +1 week window is applied, corresponding to the allowable visit window, to look for increases  $>$  2 g/dL over 3 weeks
- Hgb increase  $>$  4 g/dL over 4 weeks (+1 week)
  - Note: for programming purposes, a +1 week window is applied, corresponding to the allowable visit window, to look for increases  $>$  4 g/dL over 5 weeks.

To identify Hgb increases that meet the increase criterion above, all Hgb values taken within [AE start date – 58 days, AE start date + 15 days] will be identified. This corresponds to identifying Hgb values that occurred 4 weeks before the [AE start date – 30 days, AE start date +15 days] window of interest. HemoCue Hgb and

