### 14.6.3. Efficacy

#### 14.6.3.1. Hemoglobin Endpoints

Hemoglobin Values
Central Laboratory and HemoCue Hgb Values

 
When source of Hgb measurement is not specified: 
 
For reporting purposes, central laboratory Hgb values will be used, unless otherwise specified. However, if a central laboratory Hgb value is missing, a corresponding non-missing HemoCue Hgb value will be used. This approach will be used for the primary Hgb analysis.
 
 
 
Some displays may be created for either central laboratory Hgb values only or HemoCue Hgb values only. The central laboratory summary will be considered the primary summary in this case.
 

Evaluable Hemoglobin Values

 
Evaluable Hgb values are on-treatment Hgb values (see Section 14.4.1) that are not taken within the 8 weeks following a red blood cell transfusion, a whole blood transfusion, or a non-randomized ESA treatment which occurs on or after the randomization date.
 
Red blood cell transfusions, whole blood transfusions and non-randomized ESA treatments occurring on or after the randomization date are identified by comparing the start and stop date of the respective transfusion or ESA concomitant medication record to the randomization date.
 

Imputed Hemoglobin Values

 
For each missing value between baseline to Week 52 (inclusive), 200 imputed values will be generated using the multiple imputation method (see Section 7.1.5). The average of these 200 imputed values will be used as the value for this missing value in the summary tables and figures.
 

CONFIDENTIAL

204837

Hemoglobin Values					

 
For primary efficacy Hgb analysis and the corresponding subgroup analyses using all available observed and imputed Hgb values (on and off-treatment), Rubin's rules [Rubin, 1987] will be used to combine results of the imputed datasets using SAS PROC MIANALYZE procedure.
 
					
EP Hemoglobin Value for Primary Hgb Analysis					

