**Adverse Events**

central laboratory Hgb values will then be evaluated separately to identify increases, so that HemoCue and central laboratory Hgb values are not compared to each other to identify an increase.

For HemoCue Hgb and separately for central laboratory Hgb values, if there is a Hgb value (or daily Hgb average) within the [AE start date – 30 days, AE start date +15 days] window and an earlier Hgb value (or daily Hgb average) that is within the larger [AE start date – 58 days, AE start date + 15 days] window, and the amount of time between the two Hgb values is:

- Between 1 day and 3 weeks, inclusive, then the Hgb values will be compared to determine if there has been a Hgb increase > 2g/dL.
- Between 15 days and 5 weeks, inclusive, then the Hgb values will be compared to determine if there has been a Hgb increase > 4g/dL.

Unscheduled Hgb values will also be used in the assessment of secondary to excessive erythropoiesis following the guidance specified in Section 14.6.3 for unscheduled Hgb values and multiple Hgb values on the same date.

**Pre-defined Lists of AE Preferred Terms Corresponding with Each AESI**Thrombosis and/or tissue ischemia secondary to excessive erythropoiesis

- Narrow SMQ: Embolic and thrombotic events, arterial
- Narrow SMQ: Embolic and thrombotic events, venous
- Narrow SMQ: Embolic and thrombotic events, vessel type unspecified and mixed arterial and venous
- Broad SMQ: Thrombophlebitis
- Additional Preferred Terms:
 

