
 
○ Vascular access site occlusion
 
○ Vascular access site complication
 
○ Retinal vascular occlusion
 
○ Administration site ischaemia
 
○ Anterior segment ischaemia
 
○ Application site ischaemia
 
○ Biliary ischaemia
 
○ Bone marrow ischaemia
 
○ Brain stem ischaemia
 
○ Catheter site ischaemia
 
○ Cerebellar ischaemia
 
○ Cerebral ischaemia
 
○ ECG signs of myocardial ischaemia
 
○ Gastrointestinal ischaemia
 
○ Graft ischaemia
 
○ Hepatic ischaemia
 
○ Implant site ischaemia
 
○ Infusion site ischaemia
 
○ Injection site ischaemia
 
○ Intestinal ischaemia
 
○ Ischaemia
 
○ Macular ischaemia
 
○ Medical device site ischaemia
 
○ Myocardial ischaemia
 
	
 
○ Stoma site ischaemia
 
○ Subendocardial ischaemia
 
○ Uterine ischaemia
 
○ Vaccination site ischaemia
 
○ Vestibular ischaemia
 
○ Cerebral small vessel ischaemic disease
 
○ Colitis ischaemic
 
○ Delayed ischaemic neurological deficit
 
○ Hypoxic-ischaemic encephalopathy
 
○ Ischaemic cardiomyopathy
 
○ Ischaemic cerebral infarction
 
○ Ischaemic contracture of the left ventricle
 
○ Ischaemic enteritis
 
○ Ischaemic gastritis
 
○ Ischaemic heart disease prophylaxis
 
○ Ischaemic hepatitis
 
○ Ischaemic limb pain
 
○ Ischaemic mitral regurgitation
 
○ Ischaemic nephropathy
 
○ Ischaemic neuropathy
 
○ Ischaemic pancreatitis
 
○ Ischaemic skin ulcer
 
○ Ischaemic stroke
 
○ Necrosis ischaemic
 

--	---

CONFIDENTIAL

204837

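### The AESI for thrombosis or ischemia from excessive erythropoiesis can be met by an Hgb rise that a transfusion produced

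*SAP*

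**What the plan says.** SAP 14.6.4.3 builds this AESI in two steps. A list of MedDRA terms first picks out thrombosis and ischemia events. The list is broad and includes terms such as "Vascular access site complication". Hgb criteria then select, by the SAP's own account, only the events due to excessive erythropoiesis. The rule is that "Thrombosis and tissue ischemia events will be considered to be secondary to excessive erythropoiesis if during the window of" day −30 to day +15 around onset any one of three things is found: an Hgb of 13 g/dL or more, a rise above 2 g/dL, or a rise above 4 g/dL.

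For the rise criteria, "all Hgb values taken within [AE start date – 58 days, AE start date + 15 days] will be identified". HemoCue and central laboratory values are assessed separately. The smaller rise applies when the gap between values is as follows: "Between 1 day and 3 weeks, inclusive, then the Hgb values will be compared to determine if there has been a Hgb increase > 2g/dL". The larger rise, above 4 g/dL, has its own gap: "Between 15 days and 5 weeks, inclusive, then the Hgb values will be compared to determine if there has been a Hgb increase". Unscheduled values count. The cross-reference to Section 14.6.3 covers only unscheduled values and several values on one date.

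SAP 14.6.3.1 separately defines evaluable Hgb as on-treatment values "that are not taken within the 8 weeks following a red blood cell transfusion", a whole blood transfusion or a non-randomized ESA. SAP 7.4.1 (Hgb Variability) uses only evaluable values when it counts participants with rapid Hgb increases.

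**The concern.** Transfused red cells raise Hgb without any erythropoiesis. Only the 13 g/dL criterion carries an absolute level, and it is an alternative to the rise criteria, not an added condition. A participant who bleeds or is severely anemic, has a listed event and is transfused can meet a rise criterion while still well below the 10.0 to 11.0 g/dL target. Because the window runs to 15 days after onset, a transfusion given because of the event can create the label.

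Excessive erythropoiesis leading to thrombosis or ischemia is the first risk listed for daprodustat in Protocol 3.3.1. SAP 8.3.1 reports the AESI by arm as counts, a rate per 100 person-years and a relative risk with a 95% CI, which the figure notes in 14.10.9 describe as unadjusted. Mislabelled events would enter all of these. No medical review that would remove transfused cases is described.

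**Working it through.** **Inputs.** The window, gaps and thresholds are from SAP 14.6.4.3, and the transfusion rule for evaluable Hgb is from 14.6.3.1. Visit spacing is from Protocol Table 7 (every 2 weeks to Week 8, then every 4 weeks) and visit windows from Protocol Section 9. The transfusion pathway is from Protocol 7.9. Hgb series and the rise per unit are assumptions.

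**The plan's own figure.** The look-back to day −58 is described as 4 weeks before day −30: 30 + 28 = 58, which reproduces. (A 35-day pair ending on day −30 would need day −65, so some permitted pairs are cut off. This is a side matter.)

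**The rule.** With t in days from onset and both values from one assay, an event is flagged if any of these holds:
- Hgb(t) ≥ 13 for some t from −30 to +15
- Hgb(t2) − Hgb(t1) > 2 with 1 ≤ t2 − t1 ≤ 21
- Hgb(t2) − Hgb(t1) > 4 with 15 ≤ t2 − t1 ≤ 35

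For the rises, t2 lies from −30 to +15 and t1 is no earlier than −58.

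**Illustrative series.**

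| Hgb (g/dL) and day | Transfused | Gap (days) | Rise (g/dL) | As written | No transfusion between values required |
|---|---|---|---|---|---|
| 6.5 on −3, 8.8 on +4 | −2 | 7 | 2.3 | flagged | not flagged |
| 7.0 on +1, 9.2 on +10 | +2 | 9 | 2.2 | flagged | not flagged |
| 6.5 on −20, 10.6 on +8 | −5 | 28 | 4.1 | flagged | not flagged |
| 7.0 on −20, 9.5 on +8 | −5 | 28 | 2.5 | not flagged | not flagged |
| 7.0 on −5, 9.0 on +5 | −2 | 10 | 2.0 | not flagged | not flagged |
| 9.5 on −14, 11.8 on 0 | none | 14 | 2.3 | flagged | flagged |

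Applying the SAP's 8-week exclusion to the later value gives the same last column. In the second row the whole rise follows the event, so it cannot have caused it.

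**How a close pair arises.** To Week 8, nominal visits are 14 days apart and can meet the 2 g/dL criterion. After Week 8 they are 28 days apart, beyond 21, so only the 4 g/dL criterion applies. A pair within 21 days then needs an unscheduled value or shifted visits. The ±1 week window allows 28 − 7 = 21 days if one visit moves, and 28 − 14 = 14 if both do. The recheck in Protocol 7.9 comes at 4 ± 1 weeks (21 to 35 days). Earlier HemoCue checks are allowed but optional.

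**Transfused volume.** At an assumed 0.7, 1.0 or 1.3 g/dL per unit, two units give 1.4, 2.0 or 2.6 g/dL and three give 2.1, 3.0 or 3.9 g/dL. Two units, the most the initial intervention in Protocol 7.9 allows, exceed 2 g/dL only above 1.0 g/dL per unit.

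**The case against.** The strongest reply is that a safety screen may properly err toward inclusion. Evaluable Hgb is an on-treatment efficacy construct, so the SAP need not carry it over to an AESI. No hypothesis test depends on this label. The same risk is also read from adjudicated MI, stroke and thromboembolic events, from the composite AESI, and from the frequency of Hgb at or above 12 g/dL. The figure notes in 14.10.9 require AESI displays to be consistent within and across studies, and Protocol Section 3 plans a comparison with the once-daily study. Redefining the AESI here alone could damage that.

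The consistency argument stands, and it shapes the fix. So does the point that other readouts exist: this AESI is not the trial's only view of the risk. The over-inclusion argument does not stand, because the section states that the Hgb step is there to narrow the events. An event that fails the narrower rule stays in the general AE tables and, where it fits, in the composite AESI.

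A reader might infer that any event treated with three or more units is captured. The rule does not support that. Values 14 days before and 14 days after a transfusion are 28 days apart, so the threshold is 4 g/dL, and three units give at most 3.9 under the assumed range. A later value on day +18 is outside the window. If the low point was not measured, the recorded rise is smaller than the transfused amount.

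**Conclusion.** The rule as written can give the wrong label. A rise produced by transfusion can classify a thrombosis or ischemia event as due to excessive erythropoiesis, at Hgb well below target and even when the rise followed the event. This conflicts with the section's stated aim and differs from how the SAP treats its own Hgb-rise endpoint. That conclusion rests on the text alone; the example Hgb values only illustrate it.

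The size is unknown. A mislabelled case needs a listed term, a transfusion, and two same-assay values at a qualifying gap with the later one between day −30 and day +15. The documents give no transfusion rate, rise per unit or frequency of unscheduled Hgb. A reader might also infer that the arm with more transfusions will show a false excess, or that the arm comparison is unreliable. Either is possible, but the documents support neither a direction nor an amount. The primary and principal secondary analyses are unaffected.

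**What to change.** Add one condition to 14.6.4.3: a rise criterion is not met when a red cell or whole blood transfusion falls between the earlier and later Hgb values. State how a transfusion dated the same day as a value is handled. Keep the 13 g/dL criterion on all values.

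Report the AESI by arm under this condition and under the existing program definition, with the number of events that differ. Cross-study displays then keep a common definition, and the effect of transfusion is visible.

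The condition is narrower than the 8-week evaluable rule and does not exclude rises after a non-randomized ESA. A rise of that kind is still erythropoiesis, so it fits the label, whereas transfused cells do not.

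The cost is one sentence, a link to transfusion dates already used in 14.6.3, and one extra version of the AESI summary. The downside is that a true drug-driven rise in a transfused participant is missed in the restricted version unless Hgb reaches 13 g/dL, but it stays visible in the existing one.
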